7. RISK ANALYSIS

7.1. POTENTIAL & RESIDUAL RISKS

The risk analysis and the risk mitigation of the investigational feature are detailed in the Investigator Brochure (Appendix A). The main risks include the following:

- Anodic stimulation or fusion leading to under-estimation of the pacing threshold
- Inappropriate or absence of back up pacing leading to long ventricular cycle
- Slow VT detection temporarily turned off during the test leading to inability to detect Slow VT during the test

These risks are all mitigated by design and are considered acceptable.

The Global Product Analysis of the device supporting the feature under investigation (Ref. AR00523 and AR 00503) did not identify any significant additional risk related to device use.

The procedures required by the CIP do not differ from routine follow-up practice, except for the launch of the "In-Clinic LVAT" tests which is not expected to lead to other risks than the ones associated to standard threshold pacing tests.

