4.5	3.5-5.0
4.0	3.0-5.0
3.5	2.5 - 4.5
3.0	2.25 - 4.0
2.75	2.25 -3.5
2.5	2- 3.5
2.25	1.75-3
2.0	1.5-2.5
1.75	1.25-2.25
1.5	1.0-2.0
1.25	0.75-1.75
1	0.5-1.5
0.75	0.25-1.25
0.5	0.25-1.0

LEVEA – Statistical Analysis Plan

0.25	0.25-0.75
------	-----------

Note: if an LV test is reported to be done, but no manual threshold value is present, it will be imputed as “Missing”.

- A failed LV Vector Test: threshold value provided automatically by the algorithm is not equivalent to the manual threshold test done by the physician or adjudicated by the independent reviewer among the complete LV Vector Tests.

As values determined by the algorithm are not displayed on the programmer screen, data are stored in the electronic Real-Time Data (RTD) files that are loaded in the electronic Case Report Form (eCRF) in order to be extracted by the sponsor.

- Diagnostic accuracy is defined as an accurate adjudication by an independent reviewer of LV threshold value provided by the algorithm. The adjudication is based on capture and loss of capture analysis on electrogram strips recorded and stored during “In-Clinic LVAT” tests. The LV threshold value provided by the algorithm compared to the reviewer adjudication is considered accurate if the difference is within ± 1 step.

The “Accurate” range for the Independent Reviewer for a Algorithm (Automatic) threshold is provided in the table below:

Table 5: Equivalent ranges for Accurate LV tests
(Algorithm vs. Independent reviewer)

Threshold value obtained with the algorithm (Automatic) (in V)	Accurate Range (Independent reviewer)
>5	>5
5.0	>4.5
4.5	4.0-5.0
4.0	3.5-4.5
3.5	3.0-4.0
3.0	2.5-3.5
2.5	2.25- 3
2.25	2.0-2.5
2.0	1.75-2.25
1.75	1.5-2.0

LEVEA – Statistical Analysis Plan

1.5	1.25-1.75
1.25	1.0-1.5
1.0	0.75-1.25
0.75	0.5-1.0
0.5	0.25-0.75
0.25	0.25-0.5

- Assessment of LV pacing threshold underestimation: comparison to manual LV threshold value will be performed by comparing manual and automatic LV threshold values at each visit. An underestimated LV threshold value of “In-Clinic LVAT” feature is defined as a value result more than 2 steps below the LV threshold measured manually (meaning -0.5V if threshold<2.5V, else -1V as measured).

Table 6: Ranges for Under-estimated LV tests
(Manual vs. Algorithm)

Manual Threshold value obtained (in V)	Under-estimated if - Automatic threshold value (in V)
7	< 5
6	<4.5
5	< 4.0
4.5	<3.5
4.0	<3.0
3.5	<2.5
3.0	<2.25
2.75	<2.25
2.5	<2.0
2.25	<1.75
2.0	<1.5
1.75	<1.25

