10. SECONDARY EFFICACY ANALYSES

Secondary and Ancillary endpoints will be assessed at all visits using descriptive statistics. Point estimates and exact CI (Clopper & Pearson, 1934) will be presented wherever possible.

Whenever a Statistical test is performed for a Secondary Endpoint, it is of hypothesis generating and descriptive in nature.

10.1. ASSESSMENT OF DIAGNOSTIC ACCURACY OF “IN-CLINIC LVAT” TEST AT M0 VISIT: INDEPENDENT REVIEWER VALIDATION OF LV THRESHOLD VALUE PROVIDED BY ALGORITHM

This endpoint is the number of accurate determination of the LV pacing threshold value provided by the algorithm feature and an independent reviewer, on all LV pacing vectors and all pacing configurations available at M0 visit.

Diagnostic accuracy is defined as an accurate adjudication by an independent reviewer of LV threshold value provided by the algorithm. The adjudication is based on capture and loss of capture analysis on electrogram strips recorded and stored during “In-Clinic LVAT” tests. The LV threshold value provided by the algorithm compared to the reviewer adjudication is considered accurate if the difference is within ± 1 step (meaning ± 0.25 V if threshold < 2.5V, else ± 0.5 V as measured). The definition of an Accurate LV threshold value is provided above in Table 5.

In case the algorithm and the reviewer adjudication provide both a LV threshold value equal to “>5V” (the LV vector test has resulted in “no capture” or “threshold value higher than 5V at starting amplitude), the LV threshold value is considered accurate. Number and percentages of “accurate” and “inaccurate” matches will be presented along with the exact 95% CI (Clopper & Pearson, 1934).

This analysis will be performed on M0-ITT population.

Decomposition of Diagnostic Accuracy by LV Vector and by LV pacing configuration

Total number of attempted, completed, and accurate LV vector tests will be presented by LV vector for each LV pacing configuration.

For the LV tests performed for subjects with either IS1 and IS4 leads (six LV vectors common to IS1 and IS4), the percentage for the number of LV vector tests “attempted”, will be calculated based on the number subjects implanted with either IS1 and IS4 leads.

For the LV tests performed for patients with IS4 leads (eight LV vectors pertaining only to IS4), the percentage for the number of LV vector tests “attempted”, will be calculated based on the number of patients implanted with IS4 lead.

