13. ADDITIONAL EXPLORATORY ANALYSIS

Whenever a Statistical test is performed for an Additional Analysis, it is of hypothesis generating and descriptive in nature.

13.1. ACCURATE DETERMINATION OF HIGH PACING THRESHOLD VALUE (NO CAPTURE OR >5V) : ALGORITHM Vs. INDEPENDENT REVIEWER

All LV vector tests are done at a starting amplitude of 5V for all LV pacing configurations. Therefore, if the LV threshold value is > 5 V or if there is no capture at the starting amplitude for the tested LV vector, then the algorithm identifies the LV threshold value as a high pacing threshold “> 5V”.

Number and percentage of correct determination of high pacing threshold value (>5V) provided by the algorithm feature and an independent reviewer, on all LV pacing vectors and all LV pacing configurations available at M0 visit will be presented. Percentage will be based on all subjects included in the M0-ITT.

A Fisher exact test will be performed to test the significance of association between accurate determination provided by the algorithm feature and the independent reviewer. The two-sided p-value will be presented.

In addition, the Sensitivity and Specificity as defined below will also be presented:

i. Sensitivity or Probability (Algorithm feature = High Pacing Threshold | Independent reviewer = High Pacing Threshold) = $TP/(TP+FN)$

i. Specificity or Probability (Algorithm feature = Not High Pacing Threshold | Independent reviewer = Not High Pacing Threshold) = $TN/(FP + TN)$

13.2. ASSESSMENT OF CONSISTENCY OF “IN-CLINIC LVAT” TEST BETWEEN M0 AND M1 VISITS: COMPARISON TO MANUAL LV THRESHOLD TESTS RESULTS

At each of the two subject visits, success rate will be calculated for each LV vector and each LV pacing configuration based on M0-ITT and M1-ITT respectively. As we have up to 14 LV vectors and 3 configurations, we will have a total of 42 success rates at each M0 and M1 visits.

Null Hypothesis: The Success-rate for LV tests at M0 visit = The success rate for LV tests at M1 visit

LEVEA – Statistical Analysis Plan

Alternative Hypothesis: The Success-rate for LV tests at M0 visit \neq The success-rate for LV tests at M1 visit.

A paired t-test will be performed to test if the mean difference of the success rate over the two visits is significantly different from 0. A two-sided p-value will be presented. This will be performed by configuration and overall. The mean difference and its 95% CI will also be presented.

This analysis will be performed on ITT.

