13.4. DISTRIBUTION OF QRS BY VISIT

The QRS values collected for each subject will be presented as summary statistics by visit and overall. They will also be presented by means of a Box Plot.

The number and percentage of subjects with the following categories for QRS parameters will be presented:

- i. QRS \leqslant 100 ms
- ii. $100 < QRS \leqslant 120$ ms
- iii. QRS > 120 ms

LEVEA – Statistical Analysis Plan

This analysis will be based on EP.

13.5. DISTRIBUTION OF THE LV PACING THRESHOLD MEASURED PER LV PACING VECTOR IN “IN-CLINIC LVAT” ALGORITHM

The possible LV pacing thresholds measured by each LV pacing vector at each LV pacing configuration are: 0.25, 0.50, 0.75, 1.00, 1.25, 1.50, 1.75, 2.00, 2.25, 2.50, 3.00, 3.5, 4.00, 4.50, 5.00 .

A frequency distribution of the categories $\leq 2.5V$, $2.5V - \leq 3.5V$, $3.5V - \leq 5V$, $> 5V$, and a Histogram will be plotted by configuration and visit.

For the LV tests performed for subjects with either IS1 and IS4 leads six LV vectors common to IS1 and IS4), the percentage will be calculated based on the number of subjects implanted with either IS1 and IS4 leads.

For the LV tests performed for subjects with IS4 leads (eight LV vectors pertaining only to IS4), the percentage will be calculated based on the number of subjects implanted with IS4 lead.

This analysis will be based on ITT.

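### SAP Table 5, row 'algorithm 5.0', does not implement the ±1-step accuracy rule: it rejects reviewer 4.5 V and treats '>5V' differently from the row next to it

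*SAP*

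**What the plan says.** Protocol 4.1.3a and SAP 5.7 use a symmetric margin. In SAP 5.7 the algorithm's value "compared to the reviewer adjudication is considered accurate if the difference is within" ±1 step. SAP 10.1 gives the step in volts, ±0.25 "V if threshold < 2.5V, else" ±0.5 V, and refers to Table 5 for the definition. SAP 3.1 declares no change in analysis from the protocol.

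SAP 5.7 introduces Table 5 by saying that the accurate "range for the Independent Reviewer for a Algorithm (Automatic) threshold is provided in the table below". The top three rows of Table 5 are:

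| Algorithm (V) | Reviewer values scored accurate |
|---|---|
| >5 | >5 |
| 5.0 | >4.5 |
| 4.5 | 4.0-5.0 |

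Two other places deal with '>5V'. SAP 10.1 covers one situation: "In case the algorithm and the reviewer adjudication provide both a LV threshold value equal to" '>5V', the result is accurate. It does not mention the case where one side gives 5.0 V and the other '>5V'. SAP 13.1 makes '>5V' a class of its own. If there is no capture at the starting amplitude, or the threshold lies above 5 V, "then the algorithm identifies the LV threshold value as a high pacing threshold". The section then computes sensitivity and specificity against the same reviewer.

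**The concern.** A symmetric margin should give the same score to a pair of readings and to its mirror image. At the top of the scale Table 5 does not, and in both places the accepted member of the pair is the one where the algorithm reads lower than the reviewer. One accepted pair is algorithm 5.0 V with reviewer '>5V': the algorithm declares capture at 5 V and the reviewer sees none. Because '>5V' includes no capture and has no upper limit, this difference cannot be shown to be within one step.

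Diagnostic accuracy is the first secondary objective, and of the listed secondary objectives it is the one judged by the independent reviewer. A programmer who follows Table 5 will score some high-threshold tests contrary to the rule in the text. The result will appear in the overall rate and in the heat plots by vector and configuration.

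**Working it through.** **Inputs**

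- Scale: SAP 13.5 lists the values ("The possible LV pacing thresholds measured by each LV pacing vector at each LV pacing configuration are" 0.25 to 2.50 V by 0.25, then 3.0, 3.5, 4.0, 4.5 and 5.0). That is 10 + 5 = 15 numeric values.
- Top of scale: 5 V (SAP 13.1: "All LV vector tests are done at a starting amplitude of 5V for all LV pacing configurations"). With '>5' added there are 16 categories. I assume that the reviewer uses the same scale, as Table 5 implies.
- Rule: accurate if the two values are equal or adjacent on this scale.

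**Step 1. Reproduce the table.** The 14 rows from 0.25 to 4.5 all match the rule. For example, row 4.5 should run from 4.5 - 0.5 = 4.0 to 4.5 + 0.5 = 5.0, and it does. Row 2.5 accepts 2.25 to 3.0, its two neighbours.

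**Step 2. The two top rows.** The rule depends on how '>5' is read. Reading A takes it as the next step above 5.0. Reading B lets it match only itself.

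| Algorithm | Table 5 | Rule, reading A | Rule, reading B |
|---|---|---|---|
| 5.0 | 5.0, >5 | 4.5, 5.0, >5 | 4.5, 5.0 |
| >5 | >5 | 5.0, >5 | >5 |

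Under A, 14 of 16 rows match; under B, 15 of 16. Neither reading reproduces both top rows. Row 5.0 fails under both, and both require 4.5, since 5.0 - 0.5 = 4.5.

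**Step 3. Mirror check.** There are 16 × 15 / 2 = 120 pairs of different values. Exactly two score differently when algorithm and reviewer are swapped:

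| Algorithm, reviewer | Score | Swapped | Score |
|---|---|---|---|
| 4.5, 5.0 | accurate | 5.0, 4.5 | inaccurate |
| 5.0, >5 | accurate | >5, 5.0 | inaccurate |

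**Step 4. Size.** Let n be the number of complete tests, m the tests with algorithm 5.0 and reviewer 4.5, and k the tests with algorithm 5.0 and reviewer '>5'. Under reading B the correction changes the accuracy rate by (m - k)/n. The two parts work in opposite directions. The documents give none of these counts.

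For illustration only, assume n = 231 (the planned number for the primary endpoint; this endpoint covers all vectors and configurations, so its n will differ), 2 other misses and m = 0:

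| k | As tabulated | Corrected |
|---|---|---|
| 1 | 229/231 = 99.1% | 228/231 = 98.7% |
| 5 | 99.1% | 224/231 = 97.0% |
| 10 | 99.1% | 219/231 = 94.8% |

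Each test is worth 1/231 = 0.43 percentage points. In one heat-plot cell of 47 tests (assumed from the 47 evaluable subjects), one test is worth 1/47 = 2.1 points. It could move a cell from 43/47 = 91.5% (green) to 42/47 = 89.4% (brown), since the SAP's colours change at 90%.

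**The case against.** The case for leaving the table alone has several parts.

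- **Open top rows may be a convention.** Table 4 also leaves its top open: manual 5 accepts algorithm values above 4.0, which includes '>5'. Taking '>5' as the next step is coherent. This stands, and it is why accepting the mixed pair in both directions remains an option. It does not rescue Table 5, where row '>5' excludes 5.0.
- **The strict sign may be a slip for 4.5 or above.** The other numeric rows have inclusive limits, so this is plausible. If so, the first fault is a typing error that still needs correcting, and the second is untouched. For the same reason the pattern is not evidence of intent to favour low readings.
- **SAP 10.1 and 13.1 need not conflict.** A reader might infer that scoring algorithm 5.0 with reviewer '>5V' as accurate in 10.1 and as a false negative in 13.1 is a contradiction. It is not one in itself: a near miss can pass a tolerance rule and fail a high/not-high split. Nor does 10.1 say that '>5V' is accurate only when both sides give it.
- **The safety link is loose.** Protocol 7.1 names "Anodic stimulation or fusion leading to under-estimation of the pacing threshold" as a main risk, and a reader might infer that Table 5 hides it. The SAP measures under-estimation against the manual test, by more than 2 steps, in Table 6. Table 5 plays no part in that analysis, and 13.1 still shows the discordance with the reviewer.

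**Conclusion.** The point holds for one row of Table 5 and its neighbour. The lower limit of row 5.0 is wrong under either treatment of '>5': 4.5 V is one step from 5.0 V. The upper end is inconsistent with row '>5', and one rule has to be chosen for both.

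The weight is modest. The endpoint is secondary and descriptive, with no performance goal. The primary test uses Table 4 and does not depend on Table 5. Only tests in which the algorithm or the reviewer gives a value at the very top of the scale can be misclassified, and their number is not stated. A reader might infer a material inflation of the accuracy rate; the documents support no figure for this, and the net change could go either way, depending on m and k. The per-cell heat plots are more sensitive than the overall rate because their denominators are smaller.

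The conclusion rests on Table 5 as printed and on the reviewer using the algorithm's scale.

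**What to change.** In SAP Table 5, set the lower limit of row 5.0 to 4.5 inclusive, and state in 5.7 and 10.1 one rule for the mixed 5.0/'>5V' pair that applies in both directions.

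- **Preferred:** row 5.0 becomes 4.5-5.0 and row '>5' stays as it is, with a sentence that a numeric value on one side and '>5V' on the other is inaccurate. An open-ended category cannot be shown to lie within one step, and the pair is then scored as a miss in both 10.1 and 13.1.
- **Alternative:** accept the pair in both directions (row 5.0 = 4.5, 5.0, >5; row '>5' = 5.0, >5). This is symmetric but credits a difference of unknown size, so the count of mixed pairs should be reported beside the accuracy rate.

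The cost is one cell and one sentence, plus the matching change in the derivation (two cells under the alternative). No new data are needed. Under the preferred rule the accuracy rate may be slightly less favourable for high-threshold vectors.

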5.8. SUBGROUP DEFINITIONS

Not applicable

6. ANALYSIS POPULATION

6.1. INCLUDED POPULATION (IP)

The included population consists of all subjects included in the study who have completed “Inclusion Form”.

6.2. EVALUABLE POPULATION (EP)

The evaluable population will consist of IP excluding the subjects having a protocol deviation on “Eligibility Criteria: Right atrial, right and left ventricles lead must be implanted. Only Bipolar or quadripolar for left ventricular lead”. A subject whose termination date occurred prior to M0 visit, will be excluded from this population.

6.3. INTENTION TO TREAT POPULATION (ITT)

The Intention To Treat (ITT) population consists of all subjects from EP with at least 1 eligible complete LV Vector Tests at M0 or M1 visit.

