8.1. SAMPLE SIZE CALCULATION

The study primary objective will be met in case the null hypothesis that the success rate of the "In-Clinic LVAT" is at least than 90% is be rejected.

The statistical analysis of primary endpoint will be performed on the ITT population (see section 8.2).

A sample size of at least 231 evaluable LV pacing vectors (configuration) will provide 80% power to reject the trial null hypothesis by using a one-sided alpha 2.5% and assuming an expected success rate of 95% – configuration based. As each subject can provide data on 5 different pacing vectors, 47 (~231/5) subjects are needed for the statistical analysis. Accounting for a global attrition rate of 20%, 59 subjects shall be enrolled.

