8.2. ANALYSIS POPULATION

The analysis populations will be reviewed and determined during the Data Review meeting based on all included subjects. The included population will consist of all subjects who have completed "Inclusion Form".

The main analysis populations are:

- The Intention To Treat (ITT) population will consist of all included subjects with at least 1 eligible complete LV Vector Tests at M0 follow-up (if unavailable, M1 follow-up will be considered). This population will be used for the assessment of the primary endpoint (see section 4.1.2).
- The M0-Intention To Treat (M0-ITT) population will consist of all included subjects with at least 1 eligible complete LV Vector Tests at M0 follow-up. This population will be used for the assessment of the secondary endpoints concerning the LV test done at M0 follow-up (see section 4.1.3).
- The M1-Intention To Treat (M1-ITT) population will consist of all included subjects with at least 1 eligible complete LV Vector Tests at M1 follow-up. This population will be used for the assessment of the secondary endpoints concerning the LV test done at M1 follow-up (see section 4.1.3).
- The included population will be used for the assessment of the secondary endpoint “Applicability of the algorithm” (see section 4.1.3).
- The safety population will consist of all subjects included and implanted with Platinium SonR CRT-D 1811, 1841 or 1844. The number of subjects in each population will be mentioned in the disposition of subjects.
- Ancillary population will consist of all included subjects with at least one right ventricular pacing electrogram collected during RV A-test or RV P-test at M0 or/and M1 follow-up (see section 4.1.4).

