8.5. ANALYSIS OF PRIMARY, SECONDARY AND ANCILLARY ENDPOINTS

8.5.1. Primary endpoint

The trial null hypothesis is that the success rate of the “In-Clinic LVAT” feature is lower than 90%. The alternative hypothesis is that the success rate of the “In-Clinic LVAT” feature is at greater than or equal to 90%.

The Primary endpoint is discussed in details in Section 4.1.2.

A one-sided exact binomial test for proportion at 2.5% level of significance (alpha) will be performed to test the null hypothesis for the primary endpoint. The null hypothesis will be rejected if the p-value is less than 0.025.

Handling of Missing values/censoring/Discontinuations

The primary endpoint will primarily be based on the completed LV Vector Tests provided by the algorithm and collected at M0. If data at M0 is unavailable, then corresponding data collected at M1 will be considered. If data at both M0 and M1 is missing, no imputation will be done.

Supportive Analysis of the Primary Endpoint

- i. The estimate of the success rate will be presented along with exact 95% confidence interval (CI) (Clopper & Pearson, 1934). [2]
- ii. Bayesian analysis will be performed to calculate the probability that the success rate is greater than or equal to 90%. A non-informative prior for the success rate ($\sim \text{Beta}(1, 1)$) will be assumed. Thus, if x successes out of n completed LV vector tests is observed, then success rate will have a posterior distribution $\text{Beta}(x+1, n-x+1)$. A 95% credible interval will also be calculated for the success rate.

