2.3. SAMPLE SIZE CALCULATION

The study primary objective will be met in case the null hypothesis that the success rate of the “In-Clinic LVAT” is lower than 90% is rejected.

The following assumptions were made to calculate the sample size:

- Power = 80%
- One-sided alpha = 2.5%
- Null Hypothesis proportion of success-rate (target) = 90%

LEVEA – Statistical Analysis Plan

- Expected success-rate = 95%

With these assumptions, it is required to carry out at least 231 LV vector tests. As we will have 5 different pacing vectors for each subject, we will need 47 ($\sim 231/5$) subjects.

An attrition rate of 20% is expected for this study.

Thus the number of subjects needed to be enrolled to obtain 47 evaluable subjects = $47/(1-0.2) = 59$ subjects.

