3. DOCUMENT AND CHANGE HISTORY

3.1. CHANGES IN ANALYSIS COMPARED TO PROTOCOL

Not applicable.

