17.8. SPECIFICATIONS AND ANALYSIS DATABASE

The data management of study data will be performed according to the Data Management Plan.

The study database includes the raw individual data from the eCRFs as well as RTD data. As values determined by the algorithm are not displayed on the programmer screen, data are stored in the electronic Real-Time Data (RTD) files that are loaded in the electronic Case Report Form (eCRF) in order to be extracted by the sponsor.

Research and Development Department of LivaNova will extract the RTD files based on the document MISC10244.pdf that explains the extraction and analyses method. These extracted datasets (IPTL01_LEVEA_R&D_DB_M0_M1_LV_RV_20180112.txt) will then be transferred to LivaNova Biometry. For developing Tables, Figures and Listings, analyses datasets will then be developed using the eCRF data, Dt.sas as per the methods described in this SAP and documented in the Specification Document “ADaM_metadata.xls”, attached as an appendix (Appendix 2) to this SAP.

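### The SAP draws the primary ITT population from an evaluable population that the protocol does not contain, and its change section does not declare this

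*SAP*

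**What the plan says.** Protocol 8.2 defines the included population by a completed inclusion form. It defines the ITT population, which is assigned to the primary endpoint, as one that "will consist of all included subjects with at least 1 eligible complete LV Vector Tests at M0 follow-up", with M1 used where M0 is unavailable. No eligibility deviation removes a subject.

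The SAP keeps the included population (IP) in 6.1 and adds another set in 6.2: "The evaluable population will consist of IP excluding the subjects having a protocol deviation on" the lead criterion (right atrial, right and left ventricular leads implanted; LV lead bipolar or quadripolar only). EP also drops subjects whose termination came before the M0 visit. Under SAP 6.3, ITT "consists of all subjects from EP with at least 1 eligible complete LV Vector Tests at M0 or M1 visit". SAP 6.4 and 6.5 nest M0-ITT and M1-ITT inside that ITT.

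Protocol section 8 requires any relevant major change to the analysis to go through a protocol amendment or to be set out, with its rationale, in a dedicated SAP section. That section, SAP 3.1, reads "Not applicable".

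**The concern.** This is a single-arm study with one confirmatory test against a 90% performance goal, so the rule on whose tests count is part of that test. The SAP narrows the set on one eligibility criterion. Subjects who deviate on any other criterion, such as permanent atrial fibrillation, stay in. The SAP gives no reason for the difference, and its change section tells the reader that nothing has changed.

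A subject removed by EP may hold tests that the protocol would count. Protocol 4.1.2 and SAP Table 8 accept a VVI test where no DDD A-test is available, so a subject without an atrial lead could still supply primary data. None of the planned analyses brings such tests back. The per-protocol set (SAP 6.7) is itself built on EP, and the rerun in SAP 9.1.3 iii removes further subjects.

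The applicability endpoint moves in the same way. Protocol 8.2 bases it on the included population and SAP 10.4 on EP, again undeclared. There the exclusion of subjects terminated before M0 also matters, because it shrinks the denominator.

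**Working it through.** **1. The plan's own figures.** Inputs: "A one-sided exact binomial test for proportion at 2.5% level of significance (alpha) will be performed" (protocol 8.5.1); "Null Hypothesis proportion of success-rate (target) = 90" percent and an expected rate of 95% (SAP 2.3); 231 tests, five vectors per subject and 20% attrition (protocol 8.1).

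- Rule: find the smallest number of successes r with P(X ≥ r | n, 0.90) < 0.025. Power is then P(X ≥ r | n, 0.95).
- n = 231: r = 217, so at most 14 failures. Actual alpha 0.0239, power 0.816.
- n = 230: r = 217, power 0.737. The smallest n that reaches 80% power is 231.
- 231/5 = 46.2, rounded up to 47. 47/(1 − 0.20) = 58.75, rounded up to 59.

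All stated figures reproduce. They do not depend on whether ITT is drawn from IP or EP.

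**2. The definitions side by side.**

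| | Protocol 8.2 | SAP |
|---|---|---|
| Base for ITT, M0-ITT, M1-ITT | Included population | EP (6.2), through 6.3 to 6.5 |
| Lead-criterion deviation | Stays in | Removed |
| Other eligibility deviations | Stay in | Stay in |
| Terminated before M0 | In only with a complete test | Removed |
| Base for applicability | Included population | EP (10.4) |

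The fourth row hardly affects ITT, because a subject who left before M0 has no M0 or M1 test.

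**3. What one removed subject could do.** Assumption: 47 × 5 = 235 tests under the protocol's ITT, and one subject with five retained tests removed by EP, leaving 230. One-sided exact p-values against 0.90:

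| Failures / tests | p | Below 0.025 |
|---|---|---|
| 14 / 235 | 0.0197 | yes |
| 15 / 235 | 0.0350 | no |
| 13 / 230 | 0.0134 | yes |
| 14 / 230 | 0.0251 | no |

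- Removed subject with 2 failures in 5: 15/235 (not met) becomes 13/230 (met).
- Removed subject with 1 failure in 5: 14/235 becomes 13/230, and both meet the goal.
- Removed subject with 5 successes: 14/235 (met) becomes 14/230 (narrowly not met).

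**4. A smaller contribution.** If the LV lead has no ring electrode (an assumption), only the two LV tip vectors paired with the can or the RV coil remain, so at most 2 tests are lost and 233 stay.

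- Both failures: 15/235 becomes 13/233 (p = 0.012) and 16/235 (p = 0.058) becomes 14/233 (p = 0.022). Both flip.
- Both failures, but starting from 17/235 (p = 0.092): 15/233 has p = 0.038 and does not flip.
- Both successes: 14/235 becomes 14/233 (p = 0.022) and does not flip.

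**5. Dates.** SAP 3.2 dates version 1.0 to 19 February 2018 and lists no section 6 change in versions 1.1 or 1.2. SAP 17.8 names the extraction file "IPTL01_LEVEA_R&D_DB_M0_M1_LV_RV_20180112.txt", whose stamp reads as 12 January 2018, 38 days earlier.

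**The case against.** **The lead criterion is not arbitrary.** The preferred configuration uses atrial overdrive, which needs an atrial lead, and three of the five primary vectors use the LV ring. Lead configuration is fixed at implant, before any test outcome. This stands as a plausible rationale, but the SAP does not give it, and protocol section 8 asks for it.

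**The protocol leaves room.** Section 8.2 lets the populations be settled at the data review meeting, the synopsis speaks of eligible subjects, and protocol 4.5 and SAP 5.1 tie enrolment to meeting the criteria. This stands only in part. The review is to start from all included subjects. Protocol 4.1.3 d defines an eligible subject as one with a complete test, which matches its ITT. The enrolment rule would apply to every criterion, not one. It can also be argued that a restriction affecting nobody is not a major change, but the SAP cannot know that in advance, and it redefines the population of the only confirmatory test.

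**Transparency is partly planned.** SAP 7.1 gives the counts in each population, 7.2 tabulates deviations that lead to exclusion, and 9.1.2 lists all test results. This stands, so no further listing is needed. What is missing is the declaration and a primary test on the protocol's set.

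**A stronger reading of the dates.** A reader might infer that the exclusion was written after the results were known, or chosen because of them. The documents do not support that. A release date is not a drafting date, and a file-name stamp is not a record of extraction. SAP 17.8 describes the extraction in the future tense. The file holds algorithm values, while success also needs the manual values from the eCRF. What can be said is that the documents do not show that the exclusion was set before extraction.

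**Conclusion.** The point holds as a conflict between the two documents. The primary ITT in the SAP is not the one in the protocol, the change is undeclared for both the primary endpoint and the applicability endpoint, and no planned analysis uses the protocol's population.

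The size is uncertain and may be nil, because the documents do not say how many subjects deviate on the lead criterion. A reader might infer from step 3 that one subject can readily reverse the result. That would overstate it. A reversal needs an affected subject with retained tests and a failure count already close to 14 or 15 in about 235. The p-values rest on the assumed 235 tests and, like the planned test, treat tests as independent. The conclusion that the definitions conflict needs none of these assumptions.

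**What to change.** - In SAP 6.3 to 6.5, draw ITT, M0-ITT and M1-ITT from IP, as in protocol 8.2, and run the primary test on that ITT.
- Add the EP-based version of the primary test to SAP 9.1.3 as a sensitivity analysis.
- In SAP 3.1, declare EP as a change from the protocol, with the reason for singling out the lead criterion and the date of the decision. Include the changed denominator for applicability in 10.4, or return that denominator to IP.

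The cost is SAP wording and one extra run of the exact test. The planned 231 tests, 47 evaluable subjects and 59 enrolled do not change. If no subject deviates on the lead criterion, the primary result does not change either.
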